3.3 Additional Endpoint Assessments (already reported)

The following is a list of secondary endpoints intended to support product labeling. Statistical details are provided in another section.

- Reoperation or re-intervention within 6 months. Reoperation means any surgical procedure on the lower urinary tract to treat problems potentially related to BPH. Re-intervention means any invasive procedure (e.g., cystoscopy) to evaluate problems potentially related to BPH. Re-intervention excludes TRUS and urodynamics evaluations required by the study during follow-up.
- Evaluation of the proportion of sexually active subjects reporting a worsening of sexual function through 6 months on either the IIEF-15 or the MSHQ-EjD questionnaires
- Evaluation of the proportion of subjects meeting a composite of serious device or procedure related events defined as MAUE through 6 months
- Length of hospital stay (days) in the treatment groups
- Length of operative time (minutes) in the treatment groups, defined as time from pre-treatment visualization to insertion of indwelling catheter (IDC).
- Length of resection time (minutes) in the treatment groups, defined as start of first pedal activation to end of last pedal use for either Aquablation or TURP.

The following objectives are pre-specified but are not intended to support product labeling:

- Evaluation of proportion of subjects with Clavien-Dindo classification of Grade 2 or higher or any Grade 1 with persistent disability (e.g. ejaculatory disorder or erectile dysfunction) at 30 days, 6 months, and 1 year
- Evaluation of the proportion of subjects with Dysuria through 30 days
- Duration of catheterization (hours)
- Change in hemoglobin (gm/dl) at discharge from baseline
- Reoperation or Re-intervention within 30 days, 12 months, 24 months 36 months, 48 months, and 60 months
- Changes in the proportion of subjects using medications for BPH symptoms at month 6. An additional analysis of change in total daily dose of BPH-specific medications (e.g., alpha blockers, prostaglandin inhibitors, phosphodiesterase inhibitors, etc.) at month 6 will be performed.
- IPSS score at baseline, and 7 days, 1, 3, 6, 12, 24, 36 months, 48 months, and 60 months
- IPSS-QoL at baseline, and 7 days, 1, 3, 6, 12, 24, 36 months, 48 months, and 60 months
- Qmax at baseline, 1, 3, 6, 12, 24, 36 months and 60 months
- PVR at baseline, 1, 3, 6, 12, 24, 36 months and 60 months
- Outcome of device/procedure related serious adverse events

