4.6 Additional Endpoints

The following secondary objectives are intended to support product labeling. The endpoints will be tested in sequential fashion using the Holms step-down procedure for type-I error rate correction if and only if the primary objective passes according to the non-inferiority criteria outlined above. At the conclusion of the trial, the secondary endpoints intended for product labeling will be ordered sequentially from most significant to least significant. The endpoints will then be tested in order at adjusted levels of significance (i.e. E1: 0.05/k, E2: 0.05/k-1; E3: 0.05/k-2; E4: 0.05/k-3; E5: 0.05/k-4;, where k=number of specified endpoints). Once an endpoint fails, all following endpoints will not be tested. Following is a list of secondary endpoints intended to support product labeling:

- Evaluation of the proportion of subjects requiring re-operation and re-intervention through 6 months. The following hypothesis will be tested:

$$H: P_C - P_T > -\delta$$

where P_T and P_C represent proportions of subjects requiring re-operation or re-intervention through 6 months post treatment. The Aquablation group will be declared to be non-inferior to TURP if it can be established that the difference is within the non-inferiority margin of $\delta = 0.10$. The statistical test will be a z-test using pooled variance estimate and no continuity correction. In the case of small counts, an exact procedure will be used. Descriptive statistics and 95% confidence intervals will be calculated.

- Evaluation of the proportion of sexually active subjects reporting a worsening of sexual function through 6 months defined as a decrease of 6 points or more on the IIEF-5 (part of the IIEF-15) or a decrease of 2 points or more on the MSHQ-EjD questionnaires. The following hypothesis will be tested:

$$H_0: P_T = P_C$$

$$H_a: P_T < P_C$$

where P_T and P_C represent proportions of subjects with worsening score on the IIEF-5 and/or the MSHQ-EjD from baseline through 6 months post treatment. The statistical test for superiority will be a z-test using pooled variance estimate and no continuity correction. In the case of small counts, an exact procedure will be used. Descriptive statistics and 95% confidence intervals will be calculated.

- Evaluation of the mean length of hospital stay in the treatment groups. The following hypothesis will be tested:

$$H: \mu_T - \mu_C > 0$$

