## **6 Secondary Endpoint Assessments**

Six secondary endpoints, described below, are intended for marketing claims: 3 are based on 6-month results and 3 are based on perioperative results. Statistical testing for the 6-month secondary endpoints will only occur after data collection is complete.

Tests based on 6-month data:

1. Reoperation or re-intervention within 6 months. Reoperation means any surgical procedure on the lower urinary tract to treat problems potentially related to BPH. Re-intervention means any invasive procedure (e.g., cystoscopy) to evaluate problems potentially related to BPH. Re-intervention excludes TRUS and urodynamics, which are required study evaluations during follow-up. Re-intervention also excludes catheterization (which is not a surgical procedure) for acute urinary retention. The proportion of subjects with this endpoint will be compared using Fisher's exact test. Differences in proportions will be calculated with `testbinomial` from the `gsDesign` package. A 10% non-inferiority hypothesis (like the primary safety endpoint, of which this is a component) will be used and superiority will be explored after non-inferiority is shown.
2. The proportion of sexually active subjects reporting a worsening of sexual function through 6 months on either the IIEF or the MSHQ-EjD questionnaires. A subject is counted as having worse sexual function if IIEF-5 (part of IIEF-15) is decreased by at least 6 points or MSHQ is decreased by at least 2 points. The two-point threshold for MSHQ is close to

the value that distinguishes affected from unaffected men.\* Both IIEF and MSHQ assume that a man is sexually active. If the subject reports that he is not sexually active for the time period assessed, these threshold decreases cannot be met by definition. Differences in proportions will be calculated as described above. Superiority will be tested.

3. The proportion of subjects with major adverse urologic events (MAUE). MAUE is defined as any subject with a serious device- or serious procedure-related AE judged to be urologic through 6 months. Whether an event meets this endpoint is judged using the study's SAE definition and relatedness, both of which are adjudicated by the CEC. Differences in proportions will be calculated as described above. A 10% non-inferiority hypothesis (like the primary safety endpoint) will be used.

Tests based on perioperative data:

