## 7 Additional Endpoint Assessments

The following additional endpoints, evaluated using the PP cohort, are pre-specified but are not intended to support product labeling. Comparisons of proportions described below will be done using methods similar to those described for the reoperation/reintervention secondary endpoint. Comparisons of continuous variables will use a t test unless otherwise described. Testing of continuous variables will examine superiority, and in some cases, non-inferiority. Superiority tests will be 2-sided ( $\alpha=0.05$ ). Non-inferiority tests will be one-sided ( $\alpha=0.025$ ).

1. Proportion of subjects with Clavien-Dindo classification of Grade 2 or higher or any Grade 1 with persistent disability (e.g. ejaculatory disorder or erectile dysfunction) at 30 days, 6 months, and 1 year. 6-month and 1-year calculations will be performed only when full datasets are available. A 10% NIM will be used.

---

\* According to personal communication [name], creator of MSHQ, no published MCID for MSHQ exists.

2. Evaluation of the proportion of subjects with dysuria through the day 30 visit. Dysuria is defined as burning sensation while urinating of at least “about ½ the time” on the dysuria questionnaire. An additional comparison using proportion odds logistic regression will be performed. A 15% NIM will be used.
3. Duration of bladder catheterization (i.e., intraoperative catheter placement to removal prior to discharge) after the assigned study procedure. Duration will be compared with a t test. An NIM of ½ a day will be used.
4. Change in hemoglobin (gm/dl) (i.e., laboratory test) at discharge from baseline.
5. Reoperation or Re-intervention within 30 days, 12 months, 24 months and 36 months. For the 30-day time point, proportions will be compared with a 10% NIM. For longer time points, due to the expectation of study withdrawal, Kaplan-Meier survival analysis will be performed and a log rank test calculated.
6. Changes in the proportion of subjects using medications for BPH symptoms at month 6. Two analyses will be done. 1) an analysis of the proportion of subjects who increased doses of BPH medications or started a new BPH medication, and 2) the proportion who were able to decrease or stop doses of BPH medications. Relevant medications include alpha blockers, prostaglandin inhibitors, and phosphodiesterase inhibitors. A 10% NIM will be used.

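### Reoperation or re-intervention at 12, 24 and 36 months is tested by log-rank with no margin and no confidence interval for the difference, so a non-significant result could not support non-inferior durability

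*SAP*

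**What the plan says.** The same endpoint is handled in two ways, depending on the time point.

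- **30 days** (SAP section 7 item 5): "For the 30-day time point, proportions will be compared with a 10% NIM".
- **6 months** (SAP section 6 item 1): "A 10% non-inferiority hypothesis (like the primary safety endpoint, of which this is a component) will be used". Protocol section 4.6 also sets δ = 0.10, "where P_T and P_C represent proportions of subjects requiring re-operation or re-intervention through 6 months post treatment".
- **12, 24 and 36 months** (SAP section 7 item 5): "For longer time points, due to the expectation of study withdrawal, Kaplan-Meier survival analysis will be performed and a log rank test calculated".
- **48 and 60 months**: Protocol section 3.3 lists "Reoperation or Re-intervention within 30 days, 12 months, 24 months 36 months, 48 months, and 60 months", and neither document gives a test or margin for the two added visits.

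The introduction to SAP section 7 adds "Superiority tests will be 2-sided" (α = 0.05) and "Non-inferiority tests will be one-sided" (α = 0.025). It places these endpoints on the per-protocol cohort and outside product labeling. In the same section, item 1 carries a 10% margin on a proportion to 1 year. Item 7 holds IPSS change to the primary effectiveness margin using data to month 36, and item 8 treats IPSS-QoL similarly with a 1-point margin.

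**The concern.** The log-rank null hypothesis is that the two curves are equal. Failing to reject it says little when events are few and one arm has 59 men. The question asked of this endpoint at 30 days and 6 months is whether Aquablation is worse than TURP by less than a stated amount, and the later analysis no longer asks it.

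The reason given for the change is withdrawal. That explains why a crude proportion is unsuitable. It does not explain the loss of the margin, because a Kaplan-Meier difference with a confidence limit handles the same censoring.

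At stake is how the long-term retreatment result can be read. A non-significant log-rank test could accompany a true excess as large as the margin used earlier, and the plan commits to no interval that would show it.

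**Working it through.** **Inputs from the documents.** 177 randomized, 118 Aquablation (A) and 59 TURP (T) (SAP 5.5); 12% loss, leaving 156 evaluable (Protocol 4.4); two-sided 0.05 for superiority and one-sided 0.025 for non-inferiority (SAP 7); margin 10 points for this endpoint at 30 days and 6 months.

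**Assumed.** TURP 36-month retreatment of 3%, 5%, 10%, 15% or 20%; exponential event times; withdrawal of 5% per year (1 − 0.95³ = 14.3% by 36 months), with 0%, 12% and 25% in total as alternatives.

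**The plan's own figure.** No power or event count is stated for long-term retreatment. The design calculation for safety superiority (65% v 40%) does reproduce: 104 v 52 with continuity correction gives 80.1% power against 80% stated, and 156/0.88 = 177.3 against 177 stated. The arm sizes are therefore sound as inputs.

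**Step 1, formula check at 5% v 15%.**
- HR = ln(0.85)/ln(0.95) = 3.17, and ln HR = 1.153.
- Expected events = 118 × 0.15 + 59 × 0.05 = 20.7.
- Schoenfeld power = Φ(1.153 × √(20.7 × 2/9) − 1.96) = Φ(0.51) ≈ 70%.

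This approximation is optimistic for a large hazard ratio with few events and 2:1 allocation. Simulation gives about 50%, so the simulated figures are used below.

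**Step 2, simulated log-rank test, true excess of 10 points at 36 months, 118 v 59.** A miss is a result not significant against Aquablation at two-sided 0.05.

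| T v A | Missed, 12% total withdrawal | Missed, 5% per year |
|---|---|---|
| 3% v 13% | 43% | 44% |
| 5% v 15% | 50% | 53% |
| 10% v 20% | 64% | 65% |
| 15% v 25% | 69% | 71% |
| 20% v 30% | 73% | 73% |

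Repeat runs at 5% per year differ by about a point, so the range is best read as roughly 45% to 74%. With no withdrawal it is 41% to 74%, and with 25% it is 47% to 76%. The per-protocol cohort can only be smaller than the randomized one, which would not improve these figures.

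**Step 3, the alternative.** Let F be one minus the Kaplan-Meier estimate at 36 months. Take D = F_A − F_T with SE = √(SE_A² + SE_T²) by Greenwood, and conclude non-inferiority if D + 1.96 SE < 0.10.

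- True excess of 10 points: wrongly passes in about 2% of trials (at most about 3% in any setting run).
- Equal rates, 5% withdrawal per year: passes in about 96% of trials at 3%, 85% at 5%, 54% at 10% and 39% at 15%. At 20% with 12% total withdrawal it passes in 32%.

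The fall follows from the width of the interval. Ignoring censoring, 1.96 × √(p(1 − p)(1/118 + 1/59)) is 6.8 points at p = 5%, 9.4 at 10% and 11.2 at 15%. At 15%, even an observed difference of zero leaves the upper limit above 10.

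**The case against.** Five points can be made for the plan.

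1. **Kaplan-Meier is itself planned.** A reader might infer that the only possible output is significant or not significant. That is wrong: the curves give an estimated proportion retreated in each arm, and a 10-point excess may be visible there. The gap is the absence of a committed interval for the difference and of a margin to read it against.

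2. **Nothing says that non-significance will be taken as non-inferiority.** That is correct. The criticism concerns what the planned test can support, not a stated intention to misread it.

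3. **The endpoint is minor.** It is additional, non-labeling, on the per-protocol cohort, and outside both the success criterion and the Holm family. Nor do the documents call durability the main purpose of long-term follow-up. This stands and limits the consequence.

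4. **The 10% margin was set for 30 days and 6 months.** It is used here as a yardstick that the SAP does not itself set at 12 to 36 months. Several other additional endpoints (items 9, 10 and 13 to 16) carry no margin at all. Both points stand, but this endpoint has a margin early and loses it later, while items 7 and 8 keep theirs to month 36.

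5. **The control rates are assumed.** This also stands, which is why a range is given.

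**Conclusion.** The concern holds in a limited form. For 12, 24 and 36 months the plan has no non-inferiority comparison for retreatment. At the planned size, and for assumed TURP rates of 3% to 20%, the log-rank test would miss a true 10-point excess in roughly 45% to 74% of trials. A non-significant result therefore could not support non-inferior durability.

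It would be too strong to say that non-significance is the likely result whenever Aquablation is at or beyond the margin. At 3% v 13% the test detects the excess in about 55% of trials. At 15 points worse it does so in about 78% (5% v 20%) and 65% (10% v 25%). Failing to detect an excess smaller than 10 points is not an error by this yardstick either, since such a difference lies inside the margin.

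The figures rest on exponential event times, the assumed control rates and the withdrawal rates stated. Study success and the labeling claims are not affected.

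**What to change.** Amend SAP section 7 item 5. At 12, 24 and 36 months:

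- report the Kaplan-Meier cumulative proportion retreated in each arm, and the A minus T difference with a 95% confidence interval;
- conclude non-inferiority only if the upper limit is below a prespecified margin, either the 10% already used for this endpoint or another that is stated and justified;
- keep the log-rank test for superiority only, and state that a non-significant result is not evidence of non-inferiority.

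Through 36 months the cost is SAP wording and a few lines of code, with no new data. The statistical cost is that the conclusion may be inconclusive if retreatment reaches about 10% or more in both arms. The interval would then show that openly.

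Extension to 48 and 60 months is not simply a wording change. Protocol section 2.29 ends the urologic procedure log at the 36-month visit, and Table 2 leaves that row blank afterwards. Later events would have to come from urological adverse event reporting. The SAP should say so, and say whether that source captures the endpoint as defined, before the same analysis is applied there.

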2.16 Randomization

Subjects will be prospectively randomized into one of two treatment groups. Randomization must occur prior to surgery and only after the subject provides written informed consent, completes all baseline procedures and meets the requirements of the study inclusion and exclusion criteria. Randomization should be performed as closely as possible to the point of surgery to minimize the incidence of dropout prior to treatment.

Subjects will be randomly assigned on a two to one (2:1) basis to either the treatment group (Aquablation) or the control group (TURP). Randomization will be stratified by baseline IPSS score (<20 and ≥20) and study site. Permuted block randomization will be performed within strata. To minimize the opportunity for the sequence to be predicted, the block size will be variable and randomly chosen from small multiples of 3 (i.e. 3 or 6). The randomization schedules for all strata will be generated in advance by the contracted study statistician using a computerized random number generator. Investigational sites will not have access to the randomization schedules. Any investigator who is found to tamper with the randomization scheme will be immediately terminated from the study and his/her study site data removed from analysis; patients at such sites treated under the protocol will be followed for an additional 3 months for safety purposes only.

Administration of randomization assignments will be accomplished using a web-based electronic data system. Treatment assignment is made only after verification of proper informed consent execution and study eligibility. The study coordinator or a designee will obtain the randomization assignment per the provided randomization instructions. A copy of the randomization assignment will be maintained in the subject's file.

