4.4 Sample Size Considerations and Statistical Analyses

The WATER Study is designed as a prospective, randomized, blinded, controlled trial to demonstrate non-inferiority of the AQUABEAM System to TURP with respect to symptom improvement at 6 months. The WATER Study is designed in accordance with FDA's "Guidance for Non-Clinical and Clinical Investigation of Devices Used for the Treatment of Prostatic Hyperplasia (BPH)," published August 17, 2010.

Subjects will be randomly assigned in a 2:1 ratio to treatment with Aquablation or to treatment with TURP. The Primary Effectiveness Endpoint for this clinical trial is change in IPSS from baseline to 6-month evaluation.

Minimum enrollment (N_{\min}) in the WATER trial is 177 subjects (118 Aquablation and 59 TURP) to power at 80% for possible demonstration of superiority for the safety endpoint under an assumption of an endpoint rate of 65% in TURP and 40% in Aquablation, while including a 12% lost to follow-up rate (i.e., 156 evaluable subjects). The primary safety endpoint with 156 subjects evaluable displays over 99% power at a one-sided alpha level of 0.025 to demonstrate non-inferiority within a margin of 10% under an assumption of a true rate of events in the Aquablation group of 40% and expected rate of 65% in the TURP group.

Under an assumption of an effectiveness NIM of 4.7 points and a treatment effect of -1.5 points (i.e., mean change score in Aquablation is 1.5 points lower than TURP) with a standard deviation of 6 points, the sample size of 156 evaluable subjects provides more than 80% power in a test of non-inferiority for the primary effectiveness endpoint.

The trial will utilize a group sequential design with a single interim look and will incorporate a sample size re-estimation (SSR) at the time of the interim look based on promise for superiority on effectiveness. Methods for the SSR have been described in detail [30] [31].

An O'Brien-Fleming (OBF) alpha-spending function will be employed to control for type I error rate on the primary effectiveness endpoint. The maximum enrollment being considered is 270 total enrolled ($N_{\max} = 1.5$ times N_{\min}).

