## 5.5 Sample Size Calculation

Sample size was reported in the original study protocol. Version G proposed an NIM of 4.7 points (based on an estimated baseline score distribution). With a sample size of 177 randomized subjects (118 A and 59 T), an effect size of -1.5 points, a standard deviation of 6 and a NIM of 4.7 points, the study has adequate power for the primary effectiveness endpoint. Power for the safety endpoint was also high assuming endpoint rates of 65% in T and 40% in A, including a 12% loss to follow-up rate.

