7. IPSS change score during follow-up (1 week, 1, 3, 6, 12, 24 and 36 months). Repeated measures analysis of variance (RMANOVA) will be used, with additional models that include baseline IPSS as a covariate. This analysis accounts for all available measurements and correlation of measurements within subjects. The mean differences across groups will be determined and the confidence limits from the regression model compared with the study-specific NIM. A treatment × time interaction will be explored as well. The purpose of this analysis is to evaluate whether the IPSS change score across all time points is non-inferior in A compared to T. The same NIM will be used as described for the primary effectiveness endpoint. If non-inferiority is shown, superiority will be tested. All available time points will be used up to month 36.
8. IPSS-QoL change scores (1 week, 1, 3, 6, 12, 24 and 36 months). A similar method as that with IPSS change score will be used and a 1-point NIM will be assumed.
9. Qmax change scores at 1, 3, 6, 12, 24 and 36 months. RMANOVA will be used.
10. PVR change scores at 1, 3, 6, 12, 24 and 36 months. RMANOVA will be used.
11. Proportion of subjects with device- or procedure-related adverse event. Proportions compared as described for primary safety endpoint.
12. Pelvic pain intensity level, population mean and change score mean, measured on a 0-10 numeric rating scale. Population score distributions will be compared with a Wilcoxon signed rank test. Change scores will be compared with a Wilcoxon test or t test. A non-inferiority margin of 2 points will be used.

13. EQ-5D time trade-off index (TTO) change scores during follow-up (7 days, and 1, 3, 6, 12, 24 and 36 months). TTO will be calculated using study data combined with available country-specific norms. RMANOVA will be used.
14. ISI at baseline, at post-op, 7 days, 1, 3, and 6 months. RMANOVA will be used.
15. IIEF-15 at baseline, and 7 days, 1, 3, 6, 12, 24 and 36 months. RMANOVA will be used.
16. MSHQ-EjD at baseline, 7 days, 1, 3, 6, 12, 24 and 36 months. RMANOVA will be used.
17. WPAI:US at baseline, 7 days, 1, 3, 6, 12, 24 and 36 months. Specifically, among those subjects who are currently working, the number of hours missed due to urinary symptoms will be compared. Given a large expected number of zeroes, a non-distributional method such as Wilcoxon's test will be used.
18. Pdet@Qmax at baseline and 6 months. This continuous outcome will be evaluated with a t test.

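### SAP section 7, item 12 names a paired test (Wilcoxon signed rank) to compare pain score levels between two independent arms; it should name the rank-sum test

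*SAP*

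**What the plan says.** Item 12 of SAP section 7 defines the outcome as "Pelvic pain intensity level, population mean and change score mean, measured on a 0-10 numeric rating scale". It then gives three instructions:

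- For score levels: "Population score distributions will be compared with a Wilcoxon signed rank test".
- For change from baseline: "Change scores will be compared with a Wilcoxon test or t test".
- For the margin: "A non-inferiority margin of 2 points will be used".

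The opening paragraph of section 7 sets a default: "Comparisons of continuous variables will use a t test unless otherwise described". It also sets superiority tests two-sided at 0.05 and non-inferiority tests one-sided at 0.025, assigns these endpoints to the per-protocol cohort, and places them outside product labelling.

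The design is a parallel-group trial with 2:1 randomization to Aquablation or TURP (Protocol section 2.16), stratified by baseline IPSS and site. Neither document pairs individual Aquablation subjects with individual TURP subjects.

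**The concern.** The signed-rank test starts from a difference for each pair, d_i = x_i − y_i, ranks the absolute differences, and compares the rank sums of the positive and negative ones. Without pairs there is no d_i and so no test statistic. Two groups of different men call for the rank-sum test, which ranks all subjects together.

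Followed literally, the plan leaves the comparison of pain score levels in one of two states. Either it cannot be computed between arms, or it is computed inside each arm and answers whether pain changed over time, which is a different question. The report could then show a p-value labelled as a pain comparison that does not compare the two procedures.

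**Working it through.** The documents give no sample size, power or alpha figure specific to pain, so there is no stated figure to reproduce. The check concerns whether the test fits the data structure.

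**1. Is a between-arm comparison intended?** Item 12 does not say so in words, but four features of the SAP point that way:
- Item 12 carries a 2-point non-inferiority margin, which has meaning only for one treatment against another.
- Change from baseline has its own sentence in item 12, so the signed-rank sentence is about score levels.
- Section 7 frames tests of continuous variables as superiority and, in some cases, non-inferiority.
- Where the SAP wants a paired analysis inside one arm, it says so: item 19 confines McNemar's test to changes in each treatment group separately.

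**2. Can the named test be computed between arms?** Planning numbers serve as an illustration:
- Randomized: 118 + 59 = 177 (SAP section 5.5).
- After 12% loss: 177 × 0.88 = 155.76, in line with "156 evaluable subjects" in Protocol section 4.4.
- At 2:1: 156 × 2/3 = 104 Aquablation and 156 × 1/3 = 52 TURP.

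These are not the group sizes for item 12. Section 7 uses the per-protocol cohort, which needs evaluable data and is not imputed (SAP section 4.2), so its counts are not known in advance. With simulated scores of 104 against 52, the signed-rank routine stopped with an error because the two sets do not form pairs. The rank-sum routine ran on the same data.

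**3. Does the allocation ratio matter?** No. With 1:1 arms of equal size the routine would run, but only by treating the listing order as pairing. As an illustration, one simulated data set on the 0–10 scale was used, with assumed means of 3 and 4 and SD of 2.5. Keeping 52 of the 104 Aquablation scores and pairing them at random with the 52 TURP scores, 2,000 times, gave:

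| Method | p-value |
|---|---|
| Signed rank, arbitrary pairings, full range | 0.002 to 0.99 |
| Signed rank, arbitrary pairings, central 95% | 0.013 to 0.64 |
| Rank-sum, all 156 subjects | 0.12 |

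The result depends on a pairing that carries no information. The means and SD are assumptions, and nothing in the SAP suggests anyone would pair this way. The range illustrates why independence of the arms is the defect; it does not estimate any error in the trial.

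**4. Does the section's default rescue the sentence?** No. The t-test default yields where an item describes something else, and item 12 does so for score levels.

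**5. What in item 12 is unaffected?** The change-score comparison. A t test or a rank-sum test on change scores is a valid between-arm analysis, and the 2-point margin can be applied to the difference in mean change.

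**The case against.** There are three arguments on the other side.

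**A within-subject comparison may have been meant.** The data would allow it: the schedule in Protocol section 2.29 has a pain score taken immediately before the procedure and again at follow-up. But that is an analysis of change, which item 12 covers separately, and it cannot be set against a non-inferiority margin. This reading does not hold.

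**It is a naming slip that would correct itself.** Items 17 and 22 of the same section refer to Wilcoxon's test without the signed-rank qualifier, so the rank-sum test is the natural intent. With unequal arms the software refuses the paired test, so the error would surface rather than silently bias a result. This largely stands and limits the importance of the point. It does not make the written instruction correct.

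**Little can change now.** Pain is collected only to 3 months, and Protocol section 3.3 marks these endpoints as already reported. This also stands: a correction today is a clarification for the record.

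A reader might infer that the whole pain endpoint lacks a valid between-arm result, that the 2:1 ratio causes the problem, or that a reported pain result is wrong. The documents support none of these. The change-score analysis survives, the defect would be the same at 1:1, and neither document says which test was actually run. Leaving a choice between a Wilcoxon test and a t test for change scores is a separate and minor matter of pre-specification; item 22 has the same latitude.

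**Conclusion.** The point holds for one of the two analyses in item 12. The Wilcoxon signed-rank test is the wrong test for comparing pain score levels between Aquablation and TURP, because the arms are independent and unmatched. The change-score comparison is usable as written, apart from the unstated type of Wilcoxon test.

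The consequence is small. The endpoint supports no labelling claim, lies outside the six secondary endpoints tested by the Holm procedure (SAP section 6), and has no bearing on either primary endpoint. The conclusion rests on two readings of the text: that item 12 intends an Aquablation versus TURP comparison, as its margin implies, and that no matching exists, since none is described.

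**What to change.** In SAP section 7, item 12, replace the signed-rank test with the Wilcoxon rank-sum (Mann-Whitney) test for score distributions.

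Two optional additions in the same item:
- State that any Wilcoxon test on change scores is also the rank-sum form.
- State how the 2-point margin is judged, since a rank test of no difference does not test a margin. A two-sided 95% confidence interval for the Aquablation versus TURP difference would do. The t-based interval for mean change matches the section's default test and its one-sided 0.025 level. A Hodges-Lehmann shift estimate with its interval is an acceptable alternative.

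Because the endpoints are marked as already reported, the sponsor should also confirm which test produced the pain comparison and record it in a note to the SAP or the study report. If a paired test was run inside each arm, the between-arm comparison of score levels should be added.

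The cost is one corrected line and a check of the analysis code. No design element, sample size or primary or secondary result changes.
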